7.0 TRIAL PROCEDURES

7.1 Trial Procedures

The Trial Flow Chart - Section 6.0 summarizes the trial procedures to be performed at each visit. Individual trial procedures are described in detail below. It may be necessary to perform these procedures at unscheduled time points if deemed clinically necessary by the investigator.

7.1.1 Administrative Procedures

7.1.1.1 Informed Consent

The investigator or qualified designee must obtain documented consent from each potential subject or each subject's legally acceptable representative prior to participating in a clinical trial. Documented consent from each subject (referred to as subject consent) will also be obtained by the investigator or qualified designee.

7.1.1.1.1 General Informed Consent

Consent will be documented by the subject's dated signature on a consent form along with the dated signature of the person conducting the consent discussion.

A copy of the respective signed and dated consent forms (subject consents) will be given to the subject and subject before participation in the trial.

The initial subject informed consent forms, any subsequent revised written informed consent forms and any written information provided to the subject will receive the Ethic Committee of the Hospital del Mar approval/favorable opinion in advance of use. The subjects will be informed in a timely manner if new information becomes available that may be relevant to their willingness to continue participation in the trial. The communication of this information will be provided and documented via a revised consent form(s) or addendum to the original consent form(s) that captures the subject's dated signature.

Relevant clinical or MRI findings will be disclosed to the patient and refer for appropriate care.

Specifics about a trial and the trial population will be added to the consent form template(s) at the protocol level. Informed consent(s) will adhere to the ethics Committee requirements, applicable laws and regulations.

7.1.1.2 Inclusion/Exclusion Criteria

If it is determined that the subject does not meet the inclusion/exclusion criteria at visits, the subject will be withdrawn from the study.

7.1.1.3 Subject Identification Card

All subjects will be given a Subject Identification Card identifying them as participants in a research trial. The card will contain trial site (Hospital del Mar) contact information (including direct telephone numbers) to be utilized in the event of an emergency. The investigator or qualified designee will provide the subject with a Subject Identification Card immediately after the subject provides written informed consent.

7.1.1.4 Medical History

A medical history will be obtained by the investigator or qualified designee.

7.1.1.5 Prior and Concomitant Treatments Review

7.1.1.5.1 Prior Treatments

The investigator or qualified designee will review any prior therapeutic drug or neurostimulation use, in advance to visit 2, and record prior treatment taken by the subject within 30 days before starting the trial.

7.1.1.5.2 Concomitant Treatments

The investigator or qualified designee will record treatment(s), if any, taken by the subject during the trial. Any changes to treatment(s) (i.e., dose, frequency) will also be recorded. If the subject reports taking any prohibited treatments during the study, this will be recorded as a study deviation. Concomitant treatments will not be changed during the study, without first consulting the investigator, except in cases of medical emergencies or other obvious exceptions. Please see Section 5.5 for more details.

7.1.1.6 Assignment of Screening Number

All consented subjects will be given a unique screening number that will be used to identify the subject for all procedures that occur prior to randomization or treatment allocation. Each subject will be assigned only one screening number. Screening numbers must not be re-used for different subjects.

7.1.1.7 Assignment of Treatment/Randomization Number

All eligible subjects will be randomly allocated and will receive a treatment/randomization number. The treatment/randomization number identifies the subject for all procedures occurring after treatment allocation/randomization. Once a treatment/randomization number is assigned to a subject, it can never be re-assigned to another subject.

A single subject cannot be assigned more than 1 treatment/randomization number.

7.1.1.8 Trial Compliance (Treatment)

During stimulation visits, administration of TPS therapy will be witnessed by the investigator and/or trial staff. Accounting of trial treatment will be conducted as specified in the Trial Flow Chart.

7.1.1.9 Interactive Voice Response System/Integrated Web Response System

The investigator or designee will call/log into IVRS/IWRS as specified in the Trial Flow Chart. Upon confirmation of a subject's eligibility at Visit 2, the investigator or designee will call IVRS or log into IWRS to randomize the subject. Subjects who do not meet eligibility criteria at Visit 4 will be screen-failed in IVRS/IWRS. For all randomized subjects, the investigator or designee will continue to call/log into IVRS/IWRS as per the Trial Flow Chart. For completed or discontinued subjects, the investigator or designee will make the final call/web action into IVRS/IWRS at their last trial visit. For additional information, please refer to Section 5.3.

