Measurements & Procedures	
 1. ALSFRS-R 2. SVC 3. MRC sum score 4. Hand-held Dynamometry 5. Motor cortex excitability by TMS 6. Plasma NfL levels 7. Blood: isolation nEVs and biomarker quantification (SOD1, Ataxin 2, C90rf72, UNC13A, TDP43, stathmin 2, NfL and NfH) 8. Brain MRI for neuronavigation 9. TPS stimulations (6 sessions of 20 min each in 2 weeks)
Study Product / Intervention	Neurolith is a medical device delivering transcranial pulse stimulations under neuronavigation guidance.
Controls	ALS patients allocated to sham stimulations. Sham treated patients will be offered to receive TPS therapy in the Open Label Extension phase (OLE) of the trial for ethical purposes.
Number of Participants & Rationale	
Stage 1: n=10
 
Stage 2: n=40 (randomization 2:1 active vs sham stimulation)
 
Rationale for sample size: this is an exploratory sample likely to be informative for experience in planning for future trials.

Study Duration:	
24 months
 
Stage 1: 6 months
 
Stage 2: 3 months recruitment, 6 months randomized phase, 6 months OLE, 3-month analysis and clinical scientific report

Timelines:	
Stage 1:
 
 ● First Patient First Visit (FPFV): September 1st, 2024 ● Last Patient Last Visit (LPLV): February 1st, 2025 
Stage 2:
 
 ● First Patient First Visit (FPFV): March 1st, 2025 ● Last Patient Last Visit (LPLV): October 1st, 2026
Study Schedule:	
Patients are recruited from the ALS center at Hospital del Mar from patients diagnosed with ALS and referrals provided by the local ALS foundation (Miquel Valls Foundation)
 
Stage 1: V1: informed consent, inclusion/exclusion criteria, TMS cortex excitability, brain MRI (for neuronavigation) can be conducted at any time between Visit 1 and 2; V2: stim; V3: TMS and biomarkers assessment week 4; V4: TMS and biomarkers assessment week 8.

	Stage 2: V1: informed consent, inclusion/exclusion criteria, TMS cortex excitability, brain MRI (for neuronavigation) can be conducted at any time between Visit 1 and 2; V2: randomization and baseline; V3-5: stim, biomarkers and scales; V6-V7: open label extension
Study Center:	ALS center and Neuromodulation center. Hospital del Mar – Pompeu Fabra University, Barcelona, Spain

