6.0 TRIAL FLOW CHART

Table 3 Trial flow chart

Stage 1 Visit Number	1	2	3-5	6
Visit Title	Screen	Baseline	Stimulation	End
Scheduled Week	0	1	2-3	4
Scheduling Window by Days:	3	3	2	5
Administrative Procedures				
Informed Consent	X			
Inclusion/Exclusion Criteria	X			
Identification Card	X			
Medical History	X			
Prior Medication Review	X			
Monitor Trial Device Compliance		X	X	
Clinical Procedures Assessments				
TPS stimulations	X	X	X	
Vital Signs		X	X	X
Physical Exam		X	X	X
MRC sum score		X	X	X
Hand-held dynamometry		X	X	X
Brain MRI		X		
TMS		X		
Neurological examination	X	X	X	X
C-SSRS	X	X	X	
ALSFRS-R	X	X	X	X
Blood draw		X	X	X
SVC		X		

Stage 2 Visit Number	1	2	3-5	6-7	8	9	10-16	17-18	19
Visit Title	Screen	Rand Base	Stim	Stim FU	End DBP	Onset OLE	Stim 3	Stim FU	End OLE
Scheduled Week	0	1	2-3	8-16	16	16	16-18	26-34	34
Scheduling Window by Days:	3	3	2	2	5	7	2	2	5
Administrative Procedures									
Informed Consent	X								
Inclusion/Exclusion Criteria	X								
Identification Card	X								
Medical History	X								
Prior Medication Review	X								
Monitor Trial Device Compliance		X	X	X			X	X	
Clinical Procedures Assessments									
TPS stimulations	X	X	X	X			X	X	
Vital Signs		X	X	X	X	X	X	X	X
Physical Exam		X	X	X	X	X	X	X	X
MRC sum score		X	X	X	X	X	X	X	X
Hand-held dynamometry		X	X	X	X	X	X	X	X
Brain MRI	X								
TMS	X	X	X	X	X				
Neurological examination	X	X	X	X	X	X	X	X	X
C-SSRS	X	X	X	X			X	X	
ALSFRS-R	X	X	X	X	X	X	X	X	X
Blood draw		X	X	X	X				
SVC		X				X			

Stim: TPS stimulation (6 times in 2 weeks, 20 min each); rand: randomization; Base: baseline; DBP: double blind period; OLE: Open Label Extension

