7.1.4 Other Procedures

7.1.4.1 Withdrawal/Discontinuation

When a subject discontinues/withdraws from participation in the trial during visit 2 (before completing the three planned stimulations), all applicable activities scheduled for the end of visit 2, as outlined in Section 6.0 Trial Flow Chart, will be performed at the time of

discontinuation. Any adverse events which are present at the time of discontinuation/withdrawal will be followed in accordance with the safety requirements outlined in Section 7.2 - Assessing and Recording Adverse Events

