7.1.5.1.1 Visit 1: Screening, brain MRI, TMS and SVC

At Visit 1, subjects who provide informed consent will undergo a series of diagnostic and safety assessments to determine if they are eligible for the trial. A designated subject must also consent to participate and will be asked to complete certain assessments throughout the trial. Subjects planning to undergo elective procedures during the study (known prior to trial start) should not proceed until such procedures have been completed.

At the screening visit, medical history, use of drugs, alcohol, caffeine, smoking will be recorded. In addition urine test and the Columbia-Suicide Severity Rating Scale (C-SSRS) will be administered. The SVC will be collected by spirometry.

If the subject fulfills the inclusion criteria and signs the informed consent, a brain MRI and a TMS study will be scheduled in the following 2-7 days (always before Visit 2). Once obtained the brain MRI, it will be uploaded to the TPS device for neuronavigation purposes. TMS will be conducted for defining presence of hyper-excitability.

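### Section 7.1.1.9 screen-fails at Visit 4, after randomisation at Visit 2, and Section 7.1.1.2 and Table 2 set no limit that keeps randomised patients in ALSFRS-R follow-up to month 6

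*Protocol*

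**What the plan says.** **Randomisation and screen failure.** Section 7.1.1.9 says: "Upon confirmation of a subject's eligibility at Visit 2, the investigator or designee will call IVRS or log into IWRS to randomize the subject". Its next sentence says: "Subjects who do not meet eligibility criteria at Visit 4 will be screen-failed in IVRS/IWRS".

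**Where Visit 4 falls.** The Stage 2 schedule in the Trial Outline reads "V2: randomization and baseline; V3-5: stim, biomarkers and scales". The Stage 2 flow chart agrees: Visit 2 is in week 1, and Visits 3-5 are stimulation visits in weeks 2-3. Section 7.1.5.1.2 (Visit 2: baseline) gives the first stimulation at Visit 2.

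**Ineligibility.** Section 7.1.1.2 says: "If it is determined that the subject does not meet the inclusion/exclusion criteria at visits, the subject will be withdrawn from the study".

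**Other discontinuation.** The introduction to Section 5.8 foresees patients who stop treatment and are still monitored. In Table 2 of that section, the row for patients who can no longer participate or do not comply with trial procedures sends them out of both treatment and trial. Section 5.9 rules out replacement.

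**Assessments on leaving.** Section 7.1.4.1 covers one case: "When a subject discontinues/withdraws from participation in the trial during visit 2 (before completing the three planned stimulations"). Section 7.1.2.1.1 adds a physical and neurological examination at early discontinuation.

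**Outcome and population.** The Stage 2 primary outcome is the change in ALSFRS-R total score from baseline to month 6. Table 5 names intention-to-treat and per-protocol populations.

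**The concern.** A screen failure is a patient who is never randomised. A patient who is allocated and stimulated at Visit 2 and then screen-failed at Visit 4 is a post-randomisation exclusion under another name. If the IWRS is specified from Section 7.1.1.9, the system could record such a patient as never having entered the trial.

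The other two rules can have the same effect at any time in the blinded period. Patients removed for ineligibility or non-compliance need not resemble those who stay, and the reasons for removal may differ between active and sham. An intention-to-treat comparison protects against this only if the outcome is collected. An analysis plan can define the population and choose a missing-data method, but it cannot recover a month-6 ALSFRS-R that conduct rules prevented from being taken.

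**Working it through.** The check is a comparison of provisions. The protocol gives no rate of late-found ineligibility or non-compliance, so there is no figure to reproduce.

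**1. Is Visit 4 after allocation?** Yes, in Stage 2. Randomisation and first stimulation are at Visit 2 (week 1); Visit 4 is one of the stimulation visits in weeks 2-3, so it comes 1 to 2 weeks later (2 − 1 = 1; 3 − 1 = 2). In the Stage 1 outline, V4 is the week-8 assessment, but Stage 1 is not randomised, so that numbering does not rescue the sentence.

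**2. Does the rest of the protocol support eligibility being settled at Visit 4?** No.
- The flow chart row "Inclusion/Exclusion Criteria" is marked at Visit 1 only.
- Section 7.1.1.6 gives each patient "a unique screening number that will be used to identify the subject for all procedures that occur prior to randomization or treatment allocation". Screening status therefore ends at randomisation.
- Section 7.1.5.1.1 says "a brain MRI and a TMS study will be scheduled in the following 2-7 days (always before Visit 2"), so the TMS result needed for eligibility exists before allocation.

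All three point to a stale visit number. None of them corrects the sentence.

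**3. With the visit number set aside, can a randomised patient still be removed?** Yes, by two routes.
- *Section 7.1.1.2.* Withdrawal is mandatory and the rule is not confined to the time before randomisation. One literal trigger is the exclusion criterion on inability to tolerate TMS: the Stage 2 flow chart repeats TMS during the blinded period, and a patient who stops tolerating it could still complete an ALSFRS-R.
- *Table 2.* The non-compliance row ends trial participation as well as treatment. No row assigns the action that the Section 5.8 introduction describes, stopping treatment while monitoring continues. The prohibited-treatment row asks for documentation and consultation; only Section 5.5 mentions stopping trial therapy alone.

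Section 5.8 also lets the investigator withdraw a patient whose enrolment was inappropriate. That is discretionary, so the point does not rest on it.

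**4. Is ALSFRS-R collected after removal?** No text asks for it. Section 7.1.4.1 is limited to leaving during Visit 2 and to the activities scheduled for the end of that visit. The examination in Section 7.1.2.1.1 has no visit limit but is not an ALSFRS-R. Section 7.1.1.2 asks for nothing further.

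**5. Consequence.** Steps 1 to 4 together allow a randomised patient to leave without a month-6 ALSFRS-R, and Section 5.9 means that patient is not replaced. No count of missed ALSFRS-R assessments is given here, because the flow chart marks the scale at all of Visits 3-5 while Section 7.1.5.1.3 places it on the last day of each 6-session period. The end-of-period value is lost under either schedule.

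**The case against.** The strongest reply is that this is a visit-number slip with some loose wording around it. Section 7.1.1.9 randomises only after eligibility is confirmed and goes on to treat randomised patients as a separate group. Visit numbers are unreliable elsewhere: Sections 7.1.5.1.3 onwards number visits up to 29, while the flow chart stops at 19. A site reading the whole protocol would hardly screen-fail someone it had already stimulated. This stands as an account of how the sentence arose, and it is why the case does not depend on Visit 4 alone.

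On Section 7.1.1.2, the flow chart governs what happens at each visit and checks the criteria only at Visit 1, so the rule may be meant for screening. A reader might infer that the trial plans to re-screen randomised patients, for example by withdrawing those whose hyperexcitability resolves. The protocol does not support that: Section 2.1 ties hyperexcitability to baseline, and Section 7.1.2.1.1 sends post-treatment examination findings to adverse-event assessment. What remains is that the rule is mandatory and has no stated limit.

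On Table 2, the row also covers patients who can no longer participate, and some non-compliant patients may not supply an ALSFRS-R whatever the rule says. That stands, and it calls for splitting the row rather than simply reversing it.

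Finally, Section 8.1 calls the results descriptive, and defining intention to treat can be left to an analysis plan. Both are fair, but a descriptive comparison of arms is also affected by selective loss, and the point here concerns collecting data rather than defining a population.

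**Conclusion.** The point holds as a fault in stated conduct rules. Section 7.1.1.9 contradicts the protocol's own visit order. Separately, Section 7.1.1.2 and Table 2 can remove randomised patients before the Stage 2 primary outcome, with no provision for ALSFRS-R afterwards.

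Its size cannot be determined. The number affected may be small, and the protocol gives no basis for the amount or direction of any bias. A reader might infer a biased result or a material loss of power; neither is shown. The share of the sample that one patient represents would be the same for any dropout and does not measure these rules.

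The conclusion assumes that the rules are applied as written and that no document outside the protocol overrides them. It does not depend on whether allocation is 1:1 or 2:1, which Section 5.3 and the Trial Outline state differently. The change is worth making because it is cheap and the lost data could not be recovered later.

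**What to change.** - **Section 7.1.1.9:** screen-fail only before the randomisation call at Visit 2, and set the IWRS to match.
- **Section 7.1.1.2:** limit withdrawal for unmet criteria to before randomisation. Record ineligibility found later as a protocol deviation and keep the patient in follow-up.
- **Table 2:** split the row. Non-compliance stops treatment only; patients who cannot continue, or who withdraw consent, may leave the trial.
- **Section 7.1.4.1:** extend it to discontinuation at any visit in the blinded period and include ALSFRS-R.
- **Follow-up and analysis:** follow every randomised patient for ALSFRS-R to month 6 unless consent is withdrawn or the patient cannot take part, and analyse as randomised.

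Stopping stimulation for safety stays a clinical decision. The cost is a wording amendment, an IWRS specification change and a few additional ALSFRS-R assessments in patients who stop stimulation.

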7.1.2 Clinical Procedures/Assessments

7.1.2.1 Physical Assessments/Examinations

7.1.2.1.1 Physical Examination/Neurological Examination (PE/Neuro Exam)

A complete physical examination (PE), including a neurological exam, will be performed by a primary investigator or sub-investigator. This examination will also be performed in the event of early discontinuation. The following body systems should be included in these exams:

- Head, Eyes, Ear, Nose, and Throat
- Neck
- Cardiovascular system
- Respiratory system
- Abdomen
- Skin
- Extremities
- Neurological system (see Appendix 12.11)
- Musculoskeletal system

Examination of the breast, rectum, and urogenital system are at the investigator's discretion (i.e., clinically indicated). If a physical or neurological abnormality is noted post-treatment, the investigator will indicate whether the result is clinically significant and if it constitutes an adverse event.

7.1.2.1.3 Vital Signs

Body Temperature: Body temperature will be measured with an oral or tympanic thermometer. The same method (e.g., oral, or tympanic, °C) should be used for all measurements for each individual subject and should be the same for all subjects throughout the trial.

Heart Rate (HR), Blood Pressure (BP) and Respiratory Rate (RR): Subjects should be resting **for at least 10 minutes** prior to having vital sign measurements obtained. The **same position** should be used for all measurements for each individual subject and should be the same for all subjects throughout the trial. The correct size of the blood pressure cuff and the correct positioning on the subject's arm is essential to increase the accuracy of blood pressure measurements. The same method (e.g., manual, or automated) should be used for all measurements for each individual subject and should be the same for all subjects throughout the study.

7.1.2.1.4 Body Height/Weight

Height (cm/in) and body weight (kg/lbs.) will be collected and recorded. Measurements should be recorded to the nearest centimeter/inch and kilogram/pound. Body weight data will be collected without shoes and with heavy clothing (such as coats) removed. Body weight should be performed on the same scale for the same individual throughout the study.

7.1.2.2 Neurological and Cognitive exam

At baseline and by end of the visit 2 (stimulation) a neurological exam (as defined in section 12.6) will be administered for identifying CNS related adverse events.

7.1.2.2.2 The ALSFRS-R

The ALS Functional Rating Scale in its revised version (ALSF RS-R)³² is a disease-specific severity score that reflects motor impairment and functional deterioration in people with amyotrophic lateral sclerosis (ALS). It has been widely applied in both clinical practice and ALS research. The scale is disease-specific and encompasses 12 prompts-referred to as items-grouped into four domains to assess bulbar symptoms, limb and trunk functionality, respiratory symptoms, and the need for percutaneous endoscopic gastrostomy, non-invasive ventilation, or tracheostomy with invasive ventilation. The precursor scale was

initially developed as an outcome measure for clinical trials, but over time its revised version became commonly used in both ALS research and clinical practice

7.1.2.2.2.1. MRC sum score

The muscle strength of the limbs will be scored using the Medical Research Council (MRC) sum score, an established multifactorial scoring system with a total score between 0 and 60³³. The MRC sum score evaluates global muscle strength by combining the scores of six muscles (shoulder abductors, elbow flexors, wrist extensors, hip flexors, knee extensors, and ankle dorsiflexors) that are evaluated bilaterally.

7.1.2.2.2.2 Dynamometry

Hand-held dynamometry megascore (average of z-scores across 16 muscle groups in the arms and legs, with higher values indicating greater strength) will be obtained as described in³⁴.

7.1.2.2.3 TMS: motor threshold and excitability assessment

Studies using transcranial magnetic stimulation (TMS) have established cortical motoneuron hyperexcitability, heralded by decreased short-interval intracortical inhibition (SICI), as an early feature of sporadic and familial ALS³⁵. Greater cortical excitability is prognostic of disease progression. Motor cortex excitability has been used previously as a relevant endpoint in clinical trials in patients with ALS.³⁶ Paired-pulse transcranial magnetic stimulation (ppTMS) will be conducted in both motor cortex at each side to record: 1) motor evoked potential (MEP) amplitudes; 2) resting motor threshold; 3) intra-cortical facilitation (ICF); and 4) short intracortical inhibition (SICI)³⁷. The primary criteria for defining changes in motor excitability related with the therapy is SICI³⁶. MEP amplitude was measured at increasing stimulator strengths (eg, 120%, 140%, and 150% of RMT)

